##### 3.2.5 Safety Analysis Population

The safety analysis (SA) population will include all enrolled subjects who are treated with a study device. Similarly, for the population of special interest, i-CABG SA population will consist of SA population who are treated with a study device and undergo an i-CABG procedure.

#### 3.3 Randomization/Blinding

All subjects will be randomized in a one to one (1:1) ratio to either the control arm (SoC) or the treatment arm (SoC + DrugSorb™-ATR device). Pre-randomization stratification will be performed by study site, and by type of intended surgical procedure - either:

- CABG alone (irrespective of number of grafts); or
- All other cardiothoracic procedures (including but not limited to combination procedures [i.e., CABG + aortic/mitral valve procedures, double heart valve procedures, etc.], aortic interventions, and combination aortic + cardiac interventions).

Of note, patients undergoing undergo CABG + minor add-on procedures (e.g., left atrial appendage clipping, IABP or Impella placement, etc.) that do not (in the opinion of the investigator) significantly increase operative complexity or bleeding risk are included in the CABG alone category for Type of planned cardiothoracic surgery. Please see Section 6.1 of the CIP for additional details of pre-randomization stratification. Randomization is implemented via an Interactive Voice/Web response (IxRS) system.

Neither the subjects nor the site personnel have the treatment assignment information during the study period, unless specified in **Section 6.3** of the CIP. The blinded study team is blocked from every subject's treatment assignment before the data base lock for unblinding. Please see **Section 6.3** of the CIP for additional details of study blinding.

### 3.4 Definition of Baseline

Baseline is defined as the last non-missing value prior to the index surgical procedure.

### 3.5 Homogeneity Across Regions

In order to assess homogeneity of results across the two participating countries, assessment of country effect will be carried out for the primary effectiveness endpoint, using Cox proportional hazards regression for the first component (when deemed appropriate), logistic regression for the second components and gamma regression with log link for the third. The individual component of the primary outcome will be the dependent variable and treatment, region and their interaction will be the independent variables.

A treatment-by-country interaction that reaches the 0.05 level of significance will signal that the treatment difference on the component(s) may differ in the two countries and will be followed by an investigation of the direction and magnitude of the treatment effect in each country to assess if any interactions are qualitative in nature.

### 3.6 Homogeneity Across Subgroups of Interest

The following analysis will be carried out on the mITT, PP, i-CABG mITT, and i-CABG PP populations with no imputation for missing data.

Appropriate descriptive statistics of the primary effectiveness endpoint and its components will be presented by treatment group (treatment vs control) within the subgroup categories below. The purpose of this analysis is not to assess significance of the treatment effect (treatment vs. control on the primary effectiveness endpoint and its components) within subgroups but to assess consistency of treatment effect on the primary effectiveness endpoint and its components across subgroups.

The following is a list of the subgroups to be investigated. For each subgrouping, in order to assess homogeneity of treatment effect on the primary effectiveness endpoint and its components, assessment of treatment-by-subgroup category interaction will be carried out in a similar manner as discussed previously for assessing homogeneity across regions.

We will evaluate the consistency of effectiveness on the primary effectiveness endpoint and its components (homogeneity), in the following subgroups:

1. Sex: Male vs Female
2. Age: <65 vs.  $\geq 65$
3. CABG vs. other procedures
4. Pre-existing clinical risk factors
  - a. EuroScore II <7%;  $\geq 7\%$ )
  - b. STS mortality risk score (<4% [low], 4%-8% [intermediate], >8% [high])
  - c. Baseline thrombocytopenia (platelet count <150,000  $\mu\text{L}$  vs.  $\geq 150,000 \mu\text{L}$ )

### **3.7 Multiple Comparisons/Multiplicity**

The type I error will be controlled on the multiple outcomes on the primary and secondary effectiveness endpoints through sequential testing procedure in the following order:

Primary endpoint → Key secondary endpoint → Additional Secondary endpoints (24hr CTD → platelet transfusions → PRBC transfusions → UDPB events by class → surgical re-exploration for excessive bleeding → fatal perioperative bleeding event)

The same hierarchy will be applied to the analysis of the population of special interest (i.e., i-CABG).

The significance for the secondary endpoints will only be considered if the primary endpoint is declared statistically significant and the p-value of the previous endpoint is less than 5%, otherwise, all the subsequent p-values will be nominal.

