Type I error (alpha, α) will be preserved from inflation due to multiplicity across the primary effectiveness, key secondary, and secondary endpoints via a hierarchical closed testing step-down approach. Only in the event that preceding endpoints are declared statistically significant at the alpha 0.05 level, can further endpoints also be declared significant. The order of hierarchical testing will follow the order of primary, key secondary, and secondary endpoints as listed in the paragraph above, namely: the primary endpoint will be tested first, followed by the key secondary endpoint (percent change in pre-CPB vs. post-CPB blood ticagrelor levels), followed by the first secondary endpoint (24-hour CTD), second secondary endpoint (platelet transfusions), and lastly (PRBC transfusions). Should all preceding statistical comparisons show results below their alpha cut-off values, further secondary endpoints will be evaluated: the proportion of fatal perioperative bleeding events, proportions of UDPB events (by category), and surgical re-exploration rates.

Other exploratory endpoints include:

- Area under the concentration time curve (AUC), using the trapezoidal approach, for intraoperative ticagrelor pharmacokinetic (PK) concentration
- Operative time (measured from start of skin incision to completion of chest closure)
- Duration of ICU stay
- Duration of hospital stay
- 30-day hospital re-admissions

Details on methods of analysis for exploratory endpoints will be provided in the SAP.

Further details regarding summary and analysis of effectiveness data will be provided in the SAP.

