#### 3.2 Analysis Sets

##### 3.2.1 Modified Intent-to-Treat Population

The modified intent-to-treat (mITT) population will consist of all randomized subjects who undergo the index surgical procedure and receive a study device (whether DrugSorb™-ATR or sham). This is the primary population for all the effectiveness analyses.

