##### 3.2.4 Population of Special Interest

The isolated-CABG (i-CABG) populations will consist of mITT or PP subjects who undergo i-CABG as the index surgical procedure. The subjects who undergo all other types of surgery including valve replacement, valve repair, aortic, structural or combination of CABG plus another major procedure will be excluded. Those two populations (i-CABG mITT and i-CABG PP populations) will be used for supplementary effectiveness analyses.

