### **5 STATISTICAL ANALYSIS METHODS**

#### **5.1 General Considerations**

Unless otherwise specified, all statistical analyses will be performed on the mITT population.

In general, summary statistics (n, mean, SD, median, minimum, and maximum for continuous variables, and number and percentage of subjects in each category for categorical variables) will be provided by treatment. All summary tables will be based on the observed data unless specified otherwise. Source data for the summary tables and statistical analyses will be presented as subject level data listings.

The two-sided significance level of 5% is used for the hypothesis testing, unless specified otherwise.

Fixed sequence testing procedure will be utilized to compare the effectiveness of the treatment vs control in the following order:

Primary endpoint → Key secondary endpoint → Additional Secondary endpoints (24hr CTD → platelet transfusions → PRBC transfusions → UBPB events by class → surgical re-exploration for excessive bleeding → fatal perioperative bleeding event)

The significance for the secondary endpoints will only be considered if the primary endpoint is declared statistically significant and the p-value of the previous endpoint is less than 5%, otherwise, the testing procedure stops, and all the subsequent p-values will be nominal.

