### **5.2.4.3 i-CABG Analysis**

The primary effectiveness endpoint analysis will also be performed on the i-CABG mITT and i-CABG PP populations.

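### SAP 3.7 repeats the confirmatory testing sequence in the i-CABG population without an alpha share or a gate on the mITT primary, although other SAP sections call i-CABG supplementary

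*SAP*

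**What the plan says.** SAP 3.7 controls type I error by a fixed sequence: primary endpoint, key secondary endpoint, then the additional secondary endpoints. It continues: "The same hierarchy will be applied to the analysis of the population of special interest (i.e., i-CABG". The sentence after that is the only gate: "The significance for the secondary endpoints will only be considered if the primary endpoint is declared statistically significant", with the further condition that the preceding endpoint has p below 5%. No level is given for i-CABG, so the default in SAP 5.1 applies: "The two-sided significance level of 5% is used for the hypothesis testing, unless specified otherwise".

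Other sections give i-CABG a lower status:

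- SAP 3.2.1, on mITT: "This is the primary population for all the effectiveness analyses".
- SAP 3.2.4, on i-CABG: "Those two populations (i-CABG mITT and i-CABG PP populations) will be used for supplementary effectiveness analyses".
- SAP 5.2.4.3, under the heading for supplementary analyses: "The primary effectiveness endpoint analysis will also be performed on the i-CABG mITT and i-CABG PP populations".
- SAP 5.1 repeats the sequence with no i-CABG step.
- Protocol 11.3 controls error across endpoints only ("Only in the event that preceding endpoints are declared statistically significant at the alpha 0.05 level, can further endpoints also be declared significant"), and protocol 11.4 lists CABG alone against other surgery as a subgroup.
- SAP 3.6, which includes CABG against other procedures, says of its subgroup work: "The purpose of this analysis is not to assess significance of the treatment effect".

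**The concern.** A testing hierarchy decides which p-values may be declared significant and which are nominal. Applying it to a second population, inside the type I error section, gives that population inferential standing. Yet 3.7 supplies neither of the two things that would keep overall error at 5%: a share of alpha, or dependence on the mITT primary.

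The gating sentence does not close the gap. It restricts secondary endpoints and names no population, so nothing in it holds back the i-CABG primary test. Whether the i-CABG secondary tests are held back depends on which population's primary endpoint is meant. SAP 3.2.4 also defines two i-CABG sets (mITT and PP), and 3.7 does not say which one the hierarchy uses.

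The case that matters is a failed mITT primary with an i-CABG primary at p<0.05. No passage says that this counts as a trial claim, and none forbids it. A choice between the two readings made after unblinding would not be credible.

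**Working it through.** **Inputs.** Two-sided 0.05 (SAP 5.1, 5.2.2.1). Finkelstein-Schoenfeld statistic as defined in SAP 5.2.2.1. Effect sizes and stated power from SAP Table 1. 140 randomized for 130 evaluable at about 7% dropout (SAP 2). The i-CABG share *f* of mITT is not in the documents; 60% to 95% is assumed.

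**Step 1: the plan's own figures.** Simulating the test with independent components and normal chest tube drainage (CTD), 4,000 trials each:

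- Scenario 1 (57 per arm, SD 253): power 99.7%, stated 99.7%.
- Scenario 2 (65 per arm, SD 500): power 92.1%, stated 92.1%.
- Dropout: 130 / (1 − 0.07) = 139.8, so 140.

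The stated figures reproduce. The SAP gives no family-wise error figure for mITT together with i-CABG.

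**Step 2: error if either test can support a claim.** The i-CABG subjects are a fraction *f* of the mITT set, so under the null the two statistics are approximately bivariate normal with correlation √f. Family-wise error is

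1 − P(|Z₁| ≤ 1.96 and |Z₂| ≤ 1.96).

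Subtracting 0.05 gives the chance that i-CABG is significant while mITT is not.

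| i-CABG share *f* | √f | Family-wise error, two-sided | i-CABG significant, mITT not | Error toward benefit (nominal 2.5%) |
|---|---|---|---|---|
| 60% | 0.775 | 7.96% | 2.96% | 3.98% |
| 80% | 0.894 | 7.09% | 2.09% | 3.54% |
| 90% | 0.949 | 6.48% | 1.48% | 3.24% |
| 95% | 0.975 | 6.04% | 1.04% | 3.02% |

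The error equals 8% at a share of about 59% and 6% at about 95%. For smaller shares it rises toward the independence limit, 1 − 0.95² = 9.75%.

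**Step 3: check with the actual test.** The Finkelstein-Schoenfeld statistic was simulated under the null with 130 subjects, 1:1 within stratum, 3% fatal bleeding, 32.4% UDPB ≥2 (the mean of 24.3% and 40.5%), CTD normal with mean 640 (the mean of 480 and 800) and SD 500 floored at 0, independent components, and 30,000 runs per share. The rejection rate for mITT alone was 0.048 to 0.051. The rate for either test was 0.081, 0.069, 0.066 and 0.059 at shares of 60%, 80%, 90% and 95%. Simulated correlations were 0.776, 0.891, 0.948 and 0.977, close to √f.

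**Step 4: what an alpha split would need.** Solving Step 2 for the equal level per test that gives 5% overall, then taking mITT power from scenario 2 by a normal shift:

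- Shift = 1.960 + z(0.921) = 1.960 + 1.412 = 3.372.
- Power at level a = Φ(3.372 − z(1 − a/2)).

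| Rule | Level per test | mITT power |
|---|---|---|
| Equal split, *f* = 60% | 0.0307 | 88.7% |
| Equal split, *f* = 80% | 0.0347 | 89.6% |
| Equal split, *f* = 90% | 0.0383 | 90.3% |
| Equal split, *f* = 95% | 0.0412 | 90.8% |
| Bonferroni, any share | 0.0250 | 87.1% |

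**Step 5: position in a gated sequence.** The last step in the SAP order is fatal perioperative bleeding, tested by Fisher's exact test. At 65 per arm and the planned 3% against 3%, it is significant with probability 0.0041. An i-CABG step placed behind it would almost never be reached.

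**The case against.** The strongest reply is that the status of i-CABG is already settled. SAP 3.2.1, 3.2.4 and 5.2.4.3 agree that mITT is primary and i-CABG supplementary, and a supplementary label is the usual way to mark an analysis as non-confirmatory. On that view the sentence in 3.7 says only that i-CABG endpoints are read in the same order, with later p-values nominal after a failure. That would restrict i-CABG reporting and grant no claim.

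This reading is possible, but the SAP does not state it. The ITT and PP populations are equally supplementary (SAP 3.2.2, 3.2.3), yet 3.7 gives neither a hierarchy. Singling out i-CABG suggests more than descriptive use.

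A second reply is that the gating sentence refers to the mITT primary. Even so, it covers secondary endpoints only.

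Parts of the reply stand. The 6% to 8% is not an error rate of the plan as a whole: it needs an i-CABG result used as a claim, and an assumed share. It is two-sided; false claims of benefit would run at about 3.0% to 4.0% against 2.5%. The sentence in SAP 3.6 describes that section's own consistency analysis and does not govern 5.2.4.3, so it is weak evidence of the conflict.

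**Conclusion.** The concern holds. SAP 3.7, followed as written, allows an i-CABG primary result to be called significant after a failed mITT primary, while 3.2.4 and 5.2.4.3 make the same result supplementary. This is a conflict in a decision rule and should be fixed before unblinding. It does not show that the mITT primary test is inflated; that test keeps its 5%.

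The size is conditional: about 6% to 8% two-sided family-wise error on the primary endpoint for i-CABG shares of about 95% down to 59%, under the global null, with both tests at 0.05. The figure counts mITT and i-CABG mITT only; basing claims on i-CABG PP as well would add somewhat more. Confidence in the textual gap is high.

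**What to change.** Before unblinding, replace the i-CABG sentence in SAP 3.7 with: *All p-values in the i-CABG mITT and i-CABG PP populations are nominal and supplementary.* This agrees with SAP 3.2.4 and 5.2.4.3 and leaves mITT alpha and power unchanged. The cost is that i-CABG cannot support a stand-alone confirmatory claim if the mITT primary fails.

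If a formal i-CABG claim is wanted, name the set (i-CABG mITT) and choose one of two routes:

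1. **Gate it.** Test the i-CABG primary endpoint only after a significant mITT primary, at a stated position ahead of the fatal-bleeding test. A stand-alone claim after a failed mITT primary is again ruled out, and any endpoint placed after the i-CABG step then depends on it.
2. **Split alpha.** 0.025 per test is valid at any share and lowers scenario 2 mITT power from 92.1% to about 87%. Correlation-adjusted equal levels of 0.031 to 0.041 lower it to about 89% to 91%, but they depend on the i-CABG share.

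Because i-CABG is defined by the operation performed while randomization is stratified by the operation planned, an analysis by the planned-surgery stratum can be added as a supportive version.

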## **4 SUBJECT INFORMATION**

### **4.1 Disposition Information**

The number of subjects in each study population will be summarized by treatment. The number of subjects who did not receive a study device or were discontinued from the study will be summarized by treatment and the primary reasons for discontinuation will be provided.

### **4.2 Demographics and Baseline Characteristics**

Demographics and baseline characteristics such as sex, age, race, weight, body mass index (BMI), vital signs, and clinical laboratory data will be summarized using descriptive statistics by treatment and overall, for the mITT population.

### **4.3 Protocol Deviations**

Sites will report protocol deviations to the Sponsor. All deviations will be collected in a deviation log.

Deviations will be reviewed by blinded Sponsor representatives and characterized as major or minor in accord with the impact to the study conduct and data integrity and as outlined in the protocol deviation plan. Major deviations will be summarized and assessed by treatment and a supportive listing will be provided.

#### **4.4 Medical History**

Medical history information will be coded and summarized for the overall study and by treatment for the mITT Population using the most recent version of the Medical Dictionary for Regulatory Activities (MedDRA®).

#### **4.5 Prior and Concomitant Medications**

Prior and concomitant medications will be summarized by treatment for the mITT population using the World Health Organization-Anatomical Therapeutic Chemical classification system (WHO Drug Dictionary). Prior medications include those taken within the last 30 days but stopped prior to start of device treatment. Concomitant medications include those that started prior to device treatment (after subject randomization), but continued during treatment, as well as those that started during or after device treatment and up to the end of the 30-day follow-up period.

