6.2. Subject Randomization

All subjects will be prospectively randomized via an Interactive Voice/Web response (IxRS) system. Randomization must occur prior to the start of the cardiothoracic surgery procedure requiring CPB, but only after subject eligibility criteria is confirmed and written informed consent is provided by the subject or the subject's designated proxy. Subjects will be randomly assigned in a one to one (1:1) ratio to either the control arm (SOC) or the investigation arm (SOC + DrugSorb™-ATR device).

To ensure even distribution of subjects among the factors most likely to impact the primary and secondary outcomes they will undergo pre-randomization stratification based on study site (to account for different institutional protocols for bleeding and transfusion management), and type of surgery (isolated CABG – which generally has shorter CPB time, vs. all other cardiothoracic surgeries including combination cases – which generally require longer CPB times). Neither the investigator nor the subjects will be told their assignment prior to surgery. See below (**Section 6.3.1**) for details of the randomization assignment. A copy of the randomization assignment will be maintained in a confidential file maintained by the Randomization and Unblinding Administrator. If the subject withdraws consent following randomization but prior to surgery, the reason for failure to treat according to randomization will be recorded in the subject's study records.

To maintain the balance between sites in terms of numbers of subjects randomized, study sites will be capped at randomizing a maximum of 15% of the overall study sample. Sites may be allowed to randomize beyond the cap on a case-by-case basis in consultation with the sponsor, taking into account overall study goals, randomization balances between sites, and prior quality of data collected by the site.

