6.3.2. Study devices

All study devices will be blinded by coverage with a sterile drape. For subjects randomized to the DrugSorb™-ATR device, the unblinded perfusionist will monitor flow to ensure it stays within the protocol dictated range.

Subjects randomized to standard of care without DrugSorb™-ATR (i.e., control) will have a **sham device** in the operating room. The sham device is identical in appearance to an active DrugSorb™-ATR device. Sham devices are sealed, inactive, pre-assembled device sets containing liquid to mimic a primed, ready to use, device. They are permanently sealed and cannot be put online with the perfusion circuit. Sham devices are marked “**Not for human use**” and cannot be opened, and they will not support flow, as they are glued/sealed shut. These devices are clamped like the DrugSorb™-ATR device, but line connections are not made to it. Once installed, the sham device is covered with a sterile drape, and tubing lines approximate the positioning of the real DrugSorb™-ATR device.

Assembly of the blind space may be required in advance should the OR personnel be in the workspace during set up to preserve knowledge of treatment allocation. The FCE and/or unblinded perfusionist ensures the blind is maintained prior to, throughout, and post-surgery. Of note, the sham device and blinding scheme discussed above is identical to the model used in REFRESH II, which is an ongoing IDE study already approved by the FDA.

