9.1.1. Screening Phase and the Pre-CPB Phase

The Screening Phase through the Pre-CPB Phase is the period bound by the time that consent is provided for study participation and the start time of CPB. Subjects are qualified for study participation by confirmation of meeting all the inclusion and none of the exclusion criteria.

Each enrolled subject will be assigned a unique Subject Number consisting of a Site Number assigned by the Sponsor or designee, and a number which is sequentially assigned to all subjects screened at the investigation sites (e.g., XXX-YYY, where XXX is the site number and YYY is the subject number). The Subject Number will be used as a subject identification for each subject throughout the

investigation.

Screening and pre-CPB assessments should be completed as detailed in **Table 6**. As discussed in **Section 1.1**, all subjects undergoing CABG or with recent coronary stent placement (within prior 6 months) should have aspirin continued going into surgery. An overview of antithrombotic and anticoagulation management for study subjects is provided in Appendix 4, **Table 5**. During Screening, if consented subjects enter the Operation Phase without **post-consent** clinical chemistry, cardiac troponin, hematology, or coagulation tests to record, the last pre-consent laboratory values MAY be used.

Pre-randomization stratification

Pre-randomization stratification will be performed in on two levels (see **Section 6.1** for details):

1. By study site;
2. By the planned surgical procedure:
 - Isolated CABG (irrespective of number of grafts); or
 - All other cardiothoracic procedures.

Randomization

Subjects will be prospectively randomized in a one to one (1:1) fashion to either the control arm (SOC) or to the investigation arm (SOC + DrugSorb™-ATR device), as detailed in **Section 6.2**.

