Appendix 5: Antithrombotic Medications Allowed/Disallowed

Aspirin – allowed

Ticagrelor – allowed

Clopidogrel – any use within 7 days disallowed (as may have confounding effects on bleeding)

Prasugrel – any use within 7 days disallowed (as may have confounding effects on bleeding)

Cangrelor – any use within 4 hours of (or during) the index procedure is disallowed (as may have confounding effects on bleeding)

Argatroban – any use within 4 hours of (or during) the index procedure is disallowed

Bivalirudin – any use within 2 hours of (or during) the index procedure is disallowed

Heparin – allowed

Low molecular weight heparin (e.g., enoxaparin) and fondaparinux – allowed

DOACs (e.g., apixaban, rivaroxaban, dabigatran and edoxaban) – any use within 5 days is disallowed, as it may have confounding effects on bleeding

Warfarin – recent use disallowed unless INR < 1.5 as otherwise may have confounding effects on bleeding

Tirofiban – any use within 8 hours disallowed as may have confounding effects on bleeding (restoration of platelet function normally occurs within approximately 4 hours)¹

Eptifibatide – any use within 8 hours disallowed as may have confounding effects on bleeding (restoration of platelet function normally occurs within approximately 4 hours)¹

Abciximab – any use within 5 days disallowed as may have confounding effects on bleeding (restoration of platelet function normally occurs within approximately 72 hours)¹

References (for this appendix only):

1. Schrör K, Weber AA. Comparative Pharmacology of GP IIb/IIIa Antagonists. *J Thromb Thrombolysis*. 15:71–80.

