#### **4.6 Device/Study Exposure and Index Procedure**

Extent of exposure to study device during index operation in minutes will be calculated as:

$$(\text{device stop date/time} - \text{device start date/time})$$

Where device interruptions will be accounted for within the calculation.

Post index operation follow-up duration in days will be calculated as:

$$(\text{study exit date} - \text{device stop date}) + 1$$

Total study duration in days will be calculated similarly as:

$$(\text{study exit date} - \text{Informed consent form (ICF) date}) + 1$$

A summary of device/study exposure and index procedure information will be provided by treatment.

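### SAP 4.5 leaves medications started before randomisation and still taken at device start, such as continued aspirin, in neither the prior nor the concomitant class

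*SAP*

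**What the plan says.** SAP 4.5 defines two classes. The first is: "Prior medications include those taken within the last 30 days but stopped prior to start of device treatment". The second has two limbs: "Concomitant medications include those that started prior to device treatment (after subject randomization), but continued during treatment", and "as well as those that started during or after device treatment and up to the end of the 30-day follow-up period".

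On timing, Protocol 6.2 says: "Randomization must occur prior to the start of the cardiothoracic surgery procedure requiring CPB". Screening opens no more than two days before the day of operation (Protocol Table 6), and the code may be obtained on the day of the procedure (Protocol 6.3.1).

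On aspirin, Protocol 9.1.1 says that "all subjects undergoing CABG or with recent coronary stent placement (within prior 6 months) should have aspirin continued going into surgery". Protocol Table 5 marks aspirin at both screening and operation for subjects with ACS or a recent stent. Protocol 9.1.3 and Table 5 have subjects who were not on aspirin before surgery begin it 6 hours afterwards.

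SAP 4.6 introduces a second duration with "Post index operation follow-up duration in days will be calculated as" and computes it as study exit date minus device stop date, plus 1. Device exposure is device stop minus device start. Both feed a summary by treatment. For controls, Protocol 6.3.2 says: "Sham devices are sealed, inactive, pre-assembled device sets containing liquid to mimic a primed, ready to use, device". Protocol 9.1.2 adds that no blood passes through the sham.

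**The concern.** A prior/concomitant rule should place every recorded medication somewhere. This one has no place for a drug already running at randomisation and still running when the device starts. Because randomisation falls so close to surgery, that is the normal pattern for long-term therapy.

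This matters because the primary endpoint is bleeding and there are about 70 subjects per arm. Protocol section 10 recognises that other antithrombotics can contribute to bleeding, and Protocol 11.8 promises the incidence of prior and concomitant medications by treatment group. SAP 4.5 is the section that delivers that summary. SAP 4.2 names no antithrombotic among the baseline variables, and neither SAP subgroup list (1.3.7 and 3.6) contains one. The medication table is therefore where a reader would look to see whether the arms were balanced on antithrombotics at surgery.

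**Working it through.** There is no plan figure to reproduce. The check applies the SAP 4.5 rules to every feasible combination of start and stop.

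**Inputs**
- Prior: stopped before device start.
- Concomitant, limb A: started between randomisation and device start, and continued during treatment.
- Concomitant, limb B: started during or after device treatment.

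Start and stop each fall in one of four periods: before randomisation, randomisation to device start, during device treatment, or after it (including ongoing). Stop cannot precede start, so there are 4 + 3 + 2 + 1 = 10 patterns. Drugs stopped before randomisation are assumed to fall within the 30-day look-back.

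| Start | Stop | As written | Parenthesis removed |
|---|---|---|---|
| Before randomisation | Before randomisation | Prior | Prior |
| Before randomisation | Randomisation to device start | Prior | Prior |
| Before randomisation | During device | **Neither** | Concomitant |
| Before randomisation | After or ongoing | **Neither** | Concomitant |
| Randomisation to device start | Randomisation to device start | Prior | Prior |
| Randomisation to device start | During device | Concomitant | Concomitant |
| Randomisation to device start | After or ongoing | Concomitant | Concomitant |
| During device | During device | Concomitant | Concomitant |
| During device | After or ongoing | Concomitant | Concomitant |
| After device | After or ongoing | Concomitant | Concomitant |

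As written: 3 prior, 5 concomitant, 2 neither (3 + 5 + 2 = 10). With the parenthesis removed: 3 prior, 7 concomitant, 0 neither. These are counts of patterns, not of subjects.

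**What the aspirin row would show.** Take two illustrative subjects. One has long been on aspirin, is randomised on the day of surgery, and has one continuing aspirin entry. That is the fourth row, in neither class. The other had no aspirin before surgery and starts it 6 hours afterwards. That is the last row, concomitant. The table would count the subject without aspirin during bypass and omit the subject who had it.

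**Partial dates.** SAP 7.1 sets a partial start date to the earliest possible date and treats a missing stop date as ongoing. If only the month of surgery is known, the start becomes the first of that month, normally before randomisation. This pushes more records into the gap.

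**Sham anchors.** Active treatment starts and ends with CPB (Protocol 2.1), except that flow may end early after a device quality complaint. The sham has no flow, and neither SAP 4.5 nor SAP 4.6 says what its start or stop is. CPB duration is recorded under Table 6, and SAP 6.2 already uses CPB start to define treatment-emergent adverse events, so a clock common to both arms exists.

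**The case against.** The strongest reply is that the consequence is small. The classes feed descriptive tables only. Protocol section 10 has all medications collected in every phase, Protocol 11.8 has them listed as well as summarised, and SAP 5.1 provides subject-level listings. No exposure is lost from the data. This stands, and it limits the weight of the point.

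It can also be said that the verb in both definitions need not be exhaustive and that the parenthesis may be a loose remark. The SAP does not say so. On that reading it would give no class for a very common pattern, while SAP Appendix A 2.0 relies on independent double programming, which needs a determinate rule.

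A reader might infer more than the documents support:

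- **That heparins are omitted.** Protocol Appendix 5 lists heparin as allowed and, separately, "Low molecular weight heparin (e.g., enoxaparin) and fondaparinux – allowed". Nothing says a course begun before randomisation runs into CPB. One stopped before device start is prior; heparin begun during CPB is concomitant.
- **That control-arm quantities cannot be computed.** The term is undefined for the sham, but randomisation, CPB times, the operation date and study exit exist in both arms. Follow-up is in whole days, so the operation date serves. The eCRF is not shown and may hold a sham time.
- **That the table would show almost no perioperative aspirin.** Postoperative starts are counted. A preoperative entry closed before device start is prior, and a separate postoperative entry is concomitant.
- **That a number of missing exposures can be given.** An assumed aspirin rate of 70% to 95% would give 0.70 × 140 = 98 to 0.95 × 140 = 133 subjects. The documents give no such rate and do not show how continued aspirin is recorded.
- **That the protocol calls aspirin a confounder.** The confounding sentence in section 10 explains the prohibited list; aspirin is allowed.

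**Conclusion.** The rule is wrong as written. It leaves two of ten start/stop patterns unclassified, and continued aspirin, which the protocol expects in CABG and recent-stent subjects, falls in one of them. Heparins share the gap only if begun before randomisation and still running into CPB.

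The by-arm medication table would then be misleading on antithrombotics at surgery. This assumes that the definitions are programmed literally and that continued aspirin is held as one entry. How many subjects would be affected cannot be derived from the documents. No effectiveness test is touched. The undefined sham start and stop is a real but smaller drafting gap, since a common clock is available. Both deserve correction before the tables are programmed.

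**What to change.** 1. **SAP 4.5, classes.** Delete the parenthetical restriction to drugs begun after randomisation. Define concomitant as any medication taken on or after CPB start, through the 30-day follow-up, whatever its start date. Define prior as stopped before CPB start, with the look-back beginning 30 days before Screening, as in Protocol section 10.
2. **SAP 4.5 and the 4.6 follow-up formula, anchors.** Use CPB start and stop, or the operation date where days suffice, in both arms. Keep device start and stop for exposure in the DrugSorb arm only.
3. **Optional.** Tabulate by arm the antithrombotics ongoing at CPB start. This is an added descriptive output and is not needed to close the gap.

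The cost of items 1 and 2 is a few SAP sentences and the matching programming. The medications and CPB times are already collected. Deleting the parenthesis alone would classify all ten patterns, but would leave the sham anchors undefined.
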